5.1.4 Process Measures

All therapy sessions, including experimental sessions, may be recorded to audio and video, with all recordings preserved for research and training purposes.

Belief of condition assignment and certainty will be collected from each therapist responsible for treating the subject and the subject at the integrative session on the day after each blinded experimental session in Stage 1. These beliefs are collected as a part of the sponsor's ongoing initiative to optimize the blinding of MDMA-assisted therapy.

The Feedback Questionnaire has been developed internally by the sponsor to assess perceived benefits and harms of MDMA-assisted therapy, feedback on therapeutic

methods, and prior treatments received. The questionnaire will be completed as a self-report measure and then reviewed with the subject in order to ask follow-on questions during a semi-structured qualitative interview, which may be video recorded. This questionnaire will be completed at baseline and at the 6-month follow-up visit.

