Descriptive statistics will be computed for vital signs and subjective distress during each experimental or open-label session. The sponsor will compare pre-drug and post-drug peak blood pressure, heart rate, and body temperature during and after all experimental sessions by condition and MDMA dose. Analyses will compare peak vital signs between MDMA and placebo subjects, and a separate analysis will consider the effects of dose (0, 75, 100 or 125 mg MDMA) upon vital signs.

Frequency tables will be produced on prevalence of spontaneously reported reactions and AEs. Number and severity of spontaneously reported reactions will be compared in MDMA and placebo subjects using a one-way analysis of variance (ANOVA). The effects of MDMA dose upon number and severity of spontaneously reported reactions will also be assessed. Presence and degree of exacerbated symptoms across MDMA and placebo participant will also be examined.

Perceptions of study participation will be examined at baseline, 6-month follow-up, and end of Stage 2 using the Feedback Questionnaire and a qualitative interview. The results of this qualitative analysis will inform the sponsor of expectancies and perceptions about study procedures for future protocol development. Similarly, belief of condition assignments collected during Stage 1 will be used to assess the effectiveness of the double-blind in preparation for future studies. Results from the Feedback Questionnaire and safety data will be utilized to find the appropriate active MDMA dose for future studies.

To facilitate the planning of future studies, a preliminary estimate of effect size may be performed after all the subjects have completed the outcome assessments, one month after the second experimental session, but not all subjects have completed the six-month follow-up evaluation. This preliminary estimate will consist of safety and outcome measures. Results of the preliminary estimate will have no effect on study conduct.

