2.0 Introduction

This document presents a Statistical Analysis Plan (SAP) for MAPS study protocol MAA-1, a Phase 2 pilot clinical trial designed to evaluate the safety, feasibility, and efficacy of MDMA-assisted psychotherapy in treating social anxiety in adults on the autism spectrum.

The Multidisciplinary Association for Psychedelic Studies (MAPS) is a non-profit research and educational organization working to obtain approval for the prescription use of 3,4-methylenedioxymethamphetamine (MDMA)-assisted psychotherapy in adults on the autism spectrum with social anxiety. This is an initial pilot study to assess the efficacy of MDMA for this indication, following promising results from MAPS-sponsored studies of MDMA-assisted psychotherapy for posttraumatic stress disorder (PTSD).

The Phase 2 pilot study will examine the safety, feasibility, and efficacy of MDMA-assisted psychotherapy for social anxiety in 12 MDMA-naïve adults on the autism spectrum. This study is designed as a dose escalation study to assist with the exploration of safety and finding the most effective dose in this population. Subjects assigned to the MDMA group will receive two of three different doses, either 75 mg, 100 mg, or 125 mg MDMA. Overall, eight subjects (66.7%) will be randomized to the MDMA group and four subjects (33.3%) will be randomized to the placebo group. Subjects who received the placebo during Stage 1 will have the opportunity to cross over and take part in a second study segment, referred to as Stage 2, with two open-label experimental sessions, after completing the six-month follow-up visit at the end of Stage 1.

This study is designed to obtain safety data, and secondarily estimates of effect size for efficacy. The data will be used to determine study design and dosing for future studies for this indication. MAA-1 is also intended to contribute to the development of a manualized psychotherapeutic approach to this potential treatment. This study is exploratory. As a result, the sponsor will perform tests on all statistical comparisons without correcting for multiple comparisons.

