8.0 Analyses

In general, nominal variables will be described in terms of frequencies and percentages and analyzed using chi square analysis. Ordinal and non-normal continuous variables will be described using sample median and range, and analyzed by non-parametric statistical tests, and approximately normal variables will be described using sample mean and standard deviations and analyzed by parametric statistical tests. All statistical tests will be two-sided. All p-values will be rounded to and displayed in four decimals. If a p-value less than 0.0001 occurs it will be shown in tables as <0.0001. For any analysis that is called out as parametric, e.g. t-test, the parametric assumptions will be examined. If necessary, nonparametric analyses will be utilized, e.g. Wilcoxon rank-sum test.

Clinical data will be presented in tabular format. Data not subject to analysis according to this plan will not appear in any tables or graphs, but will be included in the data listings. Analyses will be carried out with SAS Version 9.3 or higher. Selected results may be presented graphically using standard graphical software.

Post-hoc exploratory analyses not identified in this SAP may be performed to further examine the study data. These analyses will be clearly identified as such in the final clinical study report.

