8.10.4 Safety Analyses

The primary measure of safety will be the reporting of adverse events. The Adverse events considered are Treatment Emergent Adverse Events (TEAE) defined as those AE's that occurred after dosing and those existing AEs that worsened during the study. Verbatim terms on case report forms will be mapped to preferred terms and system organ classes using the MedDRA dictionary. For incidence reporting if a subject has more than one adverse event mapped to the same preferred term, that adverse event will be reported only once using the highest severity and closest relationship to study drug. Subject incidence of adverse events will be displayed by Stage I treatment group and by system organ class. Adverse events will also be summarized by severity and relationship to study drug. Subject incidence of serious adverse events by Stage I treatment group will also be displayed. In addition to the listing of all adverse events, a listing of serious adverse events and a listing of adverse events leading to discontinuation of study drug will be included.

Summary tables of frequency listings of expected adverse events (Spontaneously Reported Reactions) mapped to preferred terms will be displayed during and after each experimental session by Stage I treatment group.

Columbia Suicide Severity Rating Scale (C-SSRS)

Suicidal ideation and behavior will be summarized according to suggestions made in the Columbia-Suicide Severity Rating Scale Scoring and Data Analysis Guide [3]. A positive response for suicidal ideation is counted when a subject answers "yes" to any one of the five suicidal ideation questions (Categories 1-5) on the C-SSRS, i.e. a score > 0 for suicidal ideation score. Serious suicidal ideation is a suicidal ideation score of 4 or 5. A positive response for suicidal behavior occurs when a subject answers "yes" to any one of the five suicidal behavior questions (Categories 6-10) on the C-SSRS, i.e. a score > 0 for suicidal behavior score. The number and percent of positive responses of Positive Ideation, Serious Ideation, and Positive Behavior will be tabulated by Stage I treatment group and time period. Compare lifetime serious suicidal ideation and positive behavior frequencies to cumulative frequencies anytime during the study until end of stage 1 and stage 2.

Subjective Units of Distress (SUD)

Descriptive statistics for SUD scores will be calculated by Stage I treatment group and time period with counts and percentages.

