Vital signs

Vital signs (heart rate, body temperature, systolic and diastolic blood pressure) will be summarized using descriptive statistics at baseline and at each post-baseline time point. Occurrences of systolic and diastolic blood pressure, heart rate, and body temperature readings above the pre-determined cutoff will be displayed with numbers and percentages by timepoint.

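### SAP 8.10.4 leaves out the by-dose safety analyses that Protocol 12.0 plans and on which the choice of future dose partly rests

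*SAP*

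**What the plan says.** Protocol 12.0 makes dose a planned dimension of the safety analysis. Pre-drug and peak vital signs are to be compared "during and after all experimental sessions by condition and MDMA dose". In addition, "a separate analysis will consider the effects of dose (0, 75, 100 or 125 mg MDMA) upon vital signs". MDMA and placebo are to be compared on peak values, and the effect of dose on how many reactions occur and how severe they are is also to be assessed. The section then gives the purpose: "Results from the Feedback Questionnaire and safety data will be utilized to find the appropriate active MDMA dose for future studies". SAP 2.0 repeats the aim of "finding the most effective dose in this population".

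SAP 8.10.4 is organised differently:

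- AEs, SAEs, C-SSRS and SUD are shown by Stage I treatment group.
- Reactions "will be displayed during and after each experimental session by Stage I treatment group".
- Vital signs "will be summarized using descriptive statistics at baseline and at each post-baseline time point". Counts above a cutoff are given by time point. Neither sentence names an arm or a dose, and peak values are not mentioned.

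For the Feedback Questionnaire, SAP 8.10.3.1 gives frequencies or summary statistics and names no grouping. Protocol 5.1.4 says of its timing: "This questionnaire will be completed at baseline and at the 6-month follow-up visit". Protocol 12.0 and the Stage 2 schedule add the end of Stage 2.

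SAP 8.0 adds: "Data not subject to analysis according to this plan will not appear in any tables or graphs". The same sentence keeps such data in the listings.

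**The concern.** Finding a dose is a stated purpose of the trial, and safety data are one of the two named sources for it. The SAP governs which tables are produced. If it omits the dose split, the analyses that the protocol prespecified for this purpose become, at best, post-hoc work under SAP 8.0 and 8.11. For vital signs, even the protocol's MDMA versus placebo comparison of peaks has no matching SAP display.

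What is at stake is the clarity of the tabulated evidence. A column that combines adjacent doses can hide a difference between them. A grouping fixed by Stage 1 assignment puts later open-label MDMA exposure under the label of the arm in which those subjects received placebo.

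**Working it through.** **1. Sessions by dose, from Table 1 (Protocol 2.4 and SAP 4.0).**

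| Dose | Stage 1 | Stage 2 (if all 4 placebo subjects cross over) | Total |
|---|---|---|---|
| 75 mg | 4 | 4 | 8 |
| 100 mg | 4 + 4 = 8 | 0 | 8 |
| 125 mg | 4 | 4 | 8 |
| Placebo | 4 × 2 = 8 | 0 | 8 |

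The MDMA total is 8 + 8 + 8 = 24, with 8 placebo sessions. This reproduces the maximum in Protocol 2.3. The Stage 1 totals, 16 MDMA and 8 placebo, match Protocol 12.0.

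**2. What treatment group can mean.** The SAP does not define it. SAP 2.0 and 5.0 describe two conditions. SAP 5.0 labels the active one as 125 mg, which disagrees with the regimens in Table 1; the two must be reconciled. SAP 8.10.1, by contrast, plans pairwise comparisons among treatment groups, which makes sense only with more than two.

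**3. Two-condition reading.** The MDMA column of the reaction table contains:

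- session 1: 4 at 75 mg + 4 at 100 mg = 8
- session 2: 4 at 100 mg + 4 at 125 mg = 8

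For illustration, take a reaction in 2 of 4 subjects at 125 mg (50%) and 0 of 4 at 100 mg. The session 2 column shows (2 + 0)/(4 + 4) = 2/8 = 25%.

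**4. Three-group reading (Group 1 active, Group 2 active, placebo).** In Stage 1 the reaction table by session then has single-dose cells: 4 at 75, 4 at 100, 4 at 100 and 4 at 125 mg. The example in step 3 disappears. The AE and SAE incidence tables have no session dimension, so each active group would still combine its two doses. Vital signs would still have no stated split.

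**5. Stage 2 under either reading.** Up to 4 + 4 = 8 open-label MDMA sessions belong to subjects whose Stage I treatment group is placebo. They are 4/8 of all 75 mg sessions and 4/8 of all 125 mg sessions. If Stage 2 were left out of these tables instead, those sessions would appear in none of them.

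**6. What a dose split could show.** With 0 events in n sessions, the two-sided exact 95% upper limit is 1 − 0.025^(1/n):

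- n = 4: 1 − 0.025^(1/4) = 60.2%
- n = 8: 1 − 0.025^(1/8) = 36.9%

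With the stages kept apart, 100 mg has 8 sessions from 8 subjects, while 75 mg and 125 mg have 4 in each stage. The 8 placebo sessions come from only 4 subjects, so the n = 8 limit does not apply to them as independent observations.

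**The case against.** The strongest reply is that the SAP is silent on the protocol's dose analyses and does not withdraw them. Protocol 12.0 still stands. Listings of all AEs, SAEs and AEs leading to discontinuation are planned, SAP 8.7 summarises dose timing and total mg, and SAP 8.0 allows post-hoc analyses. With 12 subjects, counts by dose can be rebuilt by hand. This stands. A reader might infer that the planned report cannot support a dose choice, or that a signal would be diluted in every planned output; the documents do not support either, since individual listings dilute nothing.

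A reader might also infer that vital signs on MDMA will be averaged with those on placebo. SAP 8.10.4 omits a grouping phrase but does not state pooling, and Protocol 12.0 plans the opposite. No dilution figure for vital signs is therefore justified. The by-group default in SAP 8.10 does not close the gap, because it covers efficacy and exploratory endpoints and SAP 7.2 lists vital signs as safety measures.

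A third inference is that a Feedback Questionnaire answer cannot be tied to one dose, because it follows two sessions. The items are not in the documents, a qualitative interview accompanies the questionnaire, and perceptions of dose are a stated topic. Attribution is harder, but it is not shown to be impossible.

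Finally, by-dose tables would be weak evidence. In Stage 1, 75 mg is always session 1 and 125 mg always session 2, and Groups 1 and 2 enrol in sequence. That is a reason to label the tables descriptive. It does not justify omitting a display that the protocol plans.

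**Conclusion.** The concern holds as a failure to carry protocol-planned analyses into the SAP. SAP 8.10.4 specifies no safety table by dose received, gives vital signs neither an arm nor a dose split, and relies on an undefined grouping term.

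The mixing of two doses in each Stage 1 session column, and the 2/8 illustration, depend on the two-condition reading. The SAP's explicit assignment text favours that reading, but SAP 8.10.1 leaves another open. The 2/8 is hypothetical and predicts no result. The figure of up to 8 Stage 2 MDMA sessions under the placebo label holds on either reading, provided that Stage 2 is tabulated under this grouping, all four placebo subjects cross over, and each receives both planned doses.

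This should be corrected, but it does not invalidate the trial: the data exist and the protocol's intent is clear.

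**What to change.** In the SAP:

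- Define treatment group once, and reconcile the condition label in section 5.0 with Table 1.
- In 8.10.4, add descriptive tables by dose actually received (0, 75, 100, 125 mg) for reactions, AEs with onset from the session to day 7, SUD, and vital signs (pre-drug, peak, change, number above cutoff). Show session, and keep blinded Stage 1 apart from open-label Stage 2.
- Split every vital-sign summary by arm.
- Report the Feedback Questionnaire by regimen (75 then 100 mg, 100 then 125 mg, placebo), with the end-of-Stage-2 responses shown separately.

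The cost is table shells and programming. Protocol 6.4 already requires administered doses to be logged, and SAP 8.10.3.1 already uses the dose received in each blinded session when it scores guesses. The drawback is small cells, 4 to 8 sessions per dose, with the wide limits shown above and with dose confounded with session order and enrolment cohort. The tables should carry a note saying so and should be labelled descriptive, with no tests between doses.

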8.11 Timing of Analyses

The primary efficacy analysis will be conducted after all subjects complete Stage 2. Subsequent analyses on this data set will not be conducted after initial analyses are performed, unless for further exploratory post-hoc analyses. Changes to protocol will not occur after primary analysis.

9.0 Statistical Software

Data manipulation, tabulation of descriptive statistics, calculation of inferential statistics, and graphical representations will be performed primarily using SAS (release 9.3 or higher) for Windows. If the use of other software is warranted, the final clinical study report will detail what software was used and for what purposes.

